4.2.2 Rationale for Dose Selection/Regimen/Modification

The choice of the 200 mg Q3W fixed dose is based on simulations performed using the population PK model of pembrolizumab showing that the fixed dose of 200 mg every 3 weeks will provide exposures that 1) are optimally consistent with those obtained with the 2 mg/kg dose every 3 weeks, 2) will maintain individual patient exposures in the exposure range established in melanoma as associated with maximal efficacy response and 3) will maintain individual patients exposure in the exposure range established in melanoma that are well tolerated and safe.

A fixed dose regimen will simplify the dosing regimen to be more convenient for physicians and to reduce potential for dosing errors. A fixed dosing scheme will also reduce complexity in the logistical chain at treatment facilities and reduce wastage.

The first evaluation of the safety and pharmacokinetics of pembrolizumab was in an open-label Phase I trial (Protocol 001) conducted to evaluate the safety and clinical activity of single agent pembrolizumab. The dose escalation portion of this trial evaluated three dose levels, 1 mg/kg, 3 mg/kg, and 10 mg/kg, administered every 2 weeks (Q2W) in subjects with advanced solid tumors. All three dose levels were well tolerated and no dose-limiting toxicities were observed. This first in human study of pembrolizumab showed evidence of target engagement and objective evidence of tumor size reduction at all dose levels (1 mg/kg, 3 mg/kg and 10 mg/kg Q2W). No MTD has been identified to date. Recent data from other clinical studies within the pembrolizumab program has shown that a lower dose of pembrolizumab and a less frequent schedule may be sufficient for target engagement and clinical activity.

PK data analysis of pembrolizumab administered Q2W and Q3W showed slow systemic clearance, limited volume of distribution, and a long half-life (refer to IB). Pharmacodynamic data (IL-2 release assay) suggested that peripheral target engagement is durable (>21 days), providing scientific rationale for a Q3W dosing schedule.

A population pharmacokinetic analysis has been performed using serum concentration time data from 476 patients. Within the resulting population PK model, clearance and volume parameters of pembrolizumab were found to be dependent on body weight. The relationship between clearance and body weight, with an allometric exponent of 0.59, is within the range

observed for other antibodies and would support both body weight normalized dosing or a fixed dose across all body weights. Pembrolizumab has been found to have a wide therapeutic range based on the melanoma indication. The differences in exposure for a 200 mg fixed dose regimen relative to a 2 mg/kg Q3W body weight based regimen are anticipated to remain well within the established exposure margins of 0.5 – 5.0 for pembrolizumab in the melanoma indication. The exposure margins are based on the notion of similar efficacy and safety in melanoma at 10 mg/kg Q3W vs. the proposed dose regimen of 2 mg/kg Q3W (i.e. 5-fold higher dose and exposure). The population PK evaluation revealed that there was no significant impact of tumor burden on exposure. In addition, exposure was similar between the NSCLC and melanoma indications. Therefore, there are no anticipated changes in exposure between different indication settings.

The rationale for further exploration of 2 mg/kg and comparable doses including the fixed dose of 200 mg Q3W is based on: 1) similar efficacy and safety of pembrolizumab when dosed at either 2 mg/kg or 10 mg/kg Q3W in melanoma patients, 2) the flat exposure-response relationships of pembrolizumab for both efficacy and safety in the dose ranges of 2 mg/kg Q3W to 10 mg/kg Q3W, 3) the lack of effect of tumor burden or indication on distribution behavior of pembrolizumab (as assessed by the population PK model) and 4) the assumption that the dynamics of pembrolizumab target engagement will not vary meaningfully with tumor type.

4.2.3 Rationale for Endpoints

4.2.3.1 Efficacy Endpoints

Assessing the efficacy of pembrolizumab monotherapy in untreated iBCL will be performed according to standard response criteria (see section 7.2.1.5).

Because of the possibility of pseudoprogression(16), asymptomatic patients whose tumors demonstrate radiologic progression after initial restaging may receive therapy for 3 additional cycles and then will be restaged. Because of possibility of delayed response, patients whose tumors demonstrate stable disease may also receive therapy for 3 additional cycles and then will be restaged. Patients with tumor burden which doubles in size after initial restaging will be considered hyperprogression(17) and will not be eligible for the continuation stage.

4.2.3.2 Biomarker Research

Baseline expression by tumor cells and tumor-infiltrating cells of proteins involved in the PD-1 pathway will be performed on archived samples centrally when tissue is available; expression levels will be correlated with response to therapy.

Enumeration of peripheral blood T-cell subsets will be performed with flow cytometric evaluation of peripheral blood mononuclear cells before, during, and after treatment with pembrolizumab. These analyses will identify alterations in T-cell subsets as a possible biomarker predicting response to therapy.

5.0 METHODOLOGY

5.1 Entry Criteria

5.1.1 Diagnosis/Condition for Entry into the Trial

Patients must have a confirmed diagnosis of iBCL and not have received prior treatment for it. (Prior local radiotherapy is allowed as long as measurable disease is outside prior radiation field and all radiation-related adverse events have resolved.). Prior therapy that does not include any standard agents used for treatment of FL or MZL is also allowed as long as not in the same class of drugs as pembrolizumab.) Criteria for diagnosis include histopathologic evidence for FL and MZL.

5.1.2 Subject Inclusion Criteria

In order to be eligible for participation in this trial, the subject must:

1. Be willing and able to provide written informed consent/assent for the trial.
2. Be ≥ 18 years of age on day of signing informed consent.
3. Must have measurable disease defined by at least one of the following criteria:
 - a. Lesions greater than 1.5 cm that can be accurately measured in two dimensions by CT (preferred), or MRI.
4. Must have indication for treatment (Adapted from NCCN 2015 Guidelines)
Any of the following constitute an indication for treatment:
 - a. Significant symptoms due to any iBCL: Which may include pain/discomfort, limitation of function, fatigue/malaise/constitutional symptoms, B-symptoms (fever, weight loss, night sweats), pruritus;
 - b. Threatened end-organ function due to any iBCL;
 - c. Progressive cytopenia secondary to any iBCL;
 - d. Steady progression of FL and MZL
5. Have a performance status of 0 or 1 on the ECOG Performance Scale.
6. Demonstrate adequate organ function as defined in Table 1.

Table 1 Adequate Organ Function Laboratory Values

System	Laboratory Value
Hematological	
Absolute neutrophil count (ANC)	$\geq 500/\mu\text{L}$ ^{a, b}
Platelets	$\geq 25\,000/\mu\text{L}$ ^{a, b}
Hemoglobin	$\geq 8\text{ g/dL}$ ^{a, b}
Renal	

Creatinine Measured or calculated ^a creatinine clearance (GFR can also be used in place of creatinine or CrCl)	OR $\leq 1.5 \times$ ULN $\geq 30 \text{ mL/min}$ for participant with creatinine levels $> 1.5 \times$ institutional ULN
Hepatic	
Total bilirubin	$\leq 1.5 \times$ ULN OR direct bilirubin \leq ULN for participants with total bilirubin levels $> 1.5 \times$ ULN
AST (SGOT) and ALT (SGPT)	$\leq 2.5 \times$ ULN ($\leq 5 \times$ ULN for participants with liver metastases)
Coagulation	
International normalized ratio (INR) OR prothrombin time (PT) Activated partial thromboplastin time (aPTT)	$\leq 1.5 \times$ ULN unless participant is receiving anticoagulant therapy as long as PT or PTT is within therapeutic range of intended use of anticoagulants
ALT (SGPT)=alanine aminotransferase (serum glutamic pyruvic transaminase); AST (SGOT)=aspartate aminotransferase (serum glutamic oxaloacetic transaminase); GFR=glomerular filtration rate; ULN=upper limit of normal.	
^a Growth factor and/or transfusion support is permissible to stabilize participant prior to study treatment if needed.	
^b No lower limit if cytopenia is related to bone marrow involvement.	
^c Creatinine clearance (CrCl) should be calculated per institutional standard.	
Note: This table includes eligibility-defining laboratory value requirements for treatment; laboratory value requirements should be adapted according to local regulations and guidelines for the administration of specific chemotherapies.	

7. Female subject of childbearing potential should have a negative urine or serum pregnancy within 72 hours prior to receiving the first dose of study medication. If the urine test is positive or cannot be confirmed as negative, a serum pregnancy test will be required.
8. Female subjects of childbearing potential should be willing to use 2 methods of birth control or be surgically sterile, or abstain from heterosexual activity for the course of the study through 120 days after the last dose of study medication (Reference Section 5.7.2). Subjects of childbearing potential are those who have not been surgically sterilized or have not been free from menses for > 1 year.
9. Male subjects should agree to use an adequate method of contraception starting with the first dose of study therapy through 120 days after the last dose of study therapy.

5.1.3 Subject Exclusion Criteria

The subject must be excluded from participating in the trial if the subject:

1. Is currently participating and receiving study therapy or has participated in a study of an investigational agent and received study therapy or used an investigational device within 4 weeks of the first dose of treatment.
2. Has a diagnosis of immunodeficiency or is receiving systemic steroid therapy or any other form of immunosuppressive therapy within 7 days prior to the first dose of trial treatment.

3. Has a known history of active TB (Bacillus Tuberculosis).
4. Hypersensitivity to pembrolizumab or any of its excipients.
5. Has had prior chemotherapy, radiation therapy, or immunotherapy for the diagnosis of iBCL.
6. Has a known additional malignancy that is progressing or requires active treatment. Exceptions include basal cell carcinoma of the skin or squamous cell carcinoma of the skin that has undergone potentially curative therapy or in situ cervical cancer.
7. Has known active central nervous system (CNS) metastases and/or carcinomatous meningitis.
8. Has active autoimmune disease that has required systemic treatment in the past 2 years (i.e. with use of disease modifying agents, corticosteroids or immunosuppressive drugs). Replacement therapy (e.g. thyroxine, insulin, or physiologic corticosteroid replacement therapy for adrenal or pituitary insufficiency, etc.) is not considered a form of systemic treatment.
9. Has known history of, or any evidence of active, non-infectious pneumonitis.
10. Has an active infection requiring systemic therapy.
11. Has a history or current evidence of any condition, therapy, or laboratory abnormality that might confound the results of the trial, interfere with the subject's participation for the full duration of the trial, or is not in the best interest of the subject to participate, in the opinion of the treating investigator.
12. Has known psychiatric or substance abuse disorders that would interfere with cooperation with the requirements of the trial.
13. Is pregnant or breastfeeding, or expecting to conceive or father children within the projected duration of the trial, starting with the pre-screening or screening visit through 120 days after the last dose of trial treatment.
14. Has received prior therapy with an anti-PD-1, anti-PD-L1, or anti-PD-L2 agent.
15. Has a known history of Human Immunodeficiency Virus (HIV) (HIV 1/2 antibodies).
16. Has known active Hepatitis B (e.g., HBsAg reactive) or Hepatitis C (e.g., HCV RNA [qualitative] is detected).
17. Be in urgent need of therapy for lymphoma related complications (such as hyperviscosity syndrome) and those with bulky disease.
18. Has received a live vaccine within 30 days of planned start of study therapy.

Note: Seasonal influenza vaccines for injection are generally inactivated flu vaccines and are allowed; however intranasal influenza vaccines (e.g., Flu-Mist®) are live attenuated vaccines, and are not allowed.

5.2 Trial Treatments

The treatment to be used in this trial is outlined below in **Table 2**

Table 2 Trial Treatment

Drug	Dose/Potency	Dose Frequency	Route of Administration	Regimen/Treatment Period	Use
Pembrolizumab	200 mg	Q3W	IV infusion	Day 1 of each 3 week cycle	Experimental

5.2.1 Dose Selection/Modification

5.2.1.1 Dose Selection

The rationale for selection of the dose to be used in this trial is provided in Section 4.0 – Background and Rationale.

Details on preparation and administration of pembrolizumab are provided in the Pharmacy Manual.

5.2.1.2 Dose Modification

Adverse events (both non-serious and serious) associated with pembrolizumab exposure may represent an immunologic etiology. These adverse events may occur shortly after the first dose or several months after the last dose of treatment. Pembrolizumab must be withheld for drug-related toxicities and severe or life-threatening AEs as per Table 3 below. See Section 5.6.1 and Events of Clinical Interest Guidance Document for supportive care guidelines, including use of corticosteroids.

Table 3
Dose Modification Guidelines for Drug-Related Adverse Events

General instructions:				
Immune-related AEs	Toxicity grade or conditions (CTCAEv4.0)	Action taken to pembrolizumab	irAE management with corticosteroid and/or other therapies	Monitor and follow-up
Pneumonitis	Grade 2	Withhold	
 Administer corticosteroids (initial dose of 1-2 mg/kg prednisone or equivalent) followed by taper Add prophylactic antibiotics for opportunistic infections 	
 Monitor participants for signs and symptoms of pneumonitis Evaluate participants with suspected pneumonitis with radiographic imaging and initiate corticosteroid treatment
	Grade 3 or 4, or recurrent Grade 2	Permanently discontinue		
Diarrhea / Colitis	Grade 2 or 3	Withhold	
 Administer corticosteroids (initial dose of 1-2 mg/kg prednisone or equivalent) followed by taper 	
 Monitor participants for signs and symptoms of enterocolitis (ie, diarrhea, abdominal pain, blood or mucus in stool with or without fever) and of bowel perforation (ie, peritoneal signs and ileus).

	Grade 4 or recurrent Grade 3	Permanently discontinue		
 Participants with \geq Grade 2 diarrhea suspecting colitis should consider GI consultation and performing endoscopy to rule out colitis. Participants with diarrhea/colitis should be advised to drink liberal quantities of clear fluids. If sufficient oral fluid intake is not feasible, fluid and electrolytes should be substituted via IV infusion.
AST / ALT elevation or Increased bilirubin	Grade 2 ^a	Withhold	
 Administer corticosteroids (initial dose of 0.5- 1 mg/kg prednisone or equivalent) followed by taper 	
 Monitor with liver function tests (consider weekly or more frequently until liver enzyme value returned to baseline or is stable
	Grade 3 ^b or 4 ^c	Permanently discontinue	
 Administer corticosteroids (initial dose of 1-2 mg/kg prednisone or equivalent) followed by taper 	
Type 1 diabetes mellitus (T1DM) or Hyperglycemia	Newly onset T1DM or Grade 3 or 4 hyperglycemia associated with evidence of β -cell failure	Withhold ^d	
 Initiate insulin replacement therapy for participants with T1DM Administer anti-hyperglycemic in participants with hyperglycemia 	
 Monitor participants for hyperglycemia or other signs and symptoms of diabetes.
Hypophysitis	Grade 2	Withhold	
 Administer corticosteroids and initiate hormonal replacements as clinically indicated. 	
 Monitor for signs and symptoms of hypophysitis (including hypopituitarism and adrenal insufficiency)
	Grade 3 or 4	Withhold or permanently discontinue ^d		
Hyperthyroidism	Grade 2	Continue	
 Treat with nonselective beta-blockers (eg, propranolol) or thionamides as appropriate 	
 Monitor for signs and symptoms of thyroid disorders.
	Grade 3 or 4	Withhold or permanently discontinue ^d		
Hypothyroidism	Grade 2-4	Continue	
 Initiate thyroid replacement hormones (eg, levothyroxine or liothyroinone) per standard of care 	
 Monitor for signs and symptoms of thyroid disorders.

Nephritis grading according to increased creatinine or acute kidney injury	Grade 2	Withhold	
 Administer corticosteroids (prednisone 1 to 2 mg/kg or equivalent) followed by taper. 	
 Monitor changes of renal function
	Grade 3 or 4	Permanently discontinue		
Neurological Toxicities	Grade 3 or 4	Permanently discontinue	
 Based on severity of AE administer corticosteroids 	
 Ensure adequate evaluation to confirm etiology and/or exclude other causes
Myocarditis	Grade 1	Withhold	
 Based on severity of AE administer corticosteroids 	
 Ensure adequate evaluation to confirm etiology and/or exclude other causes
	Grade 2, 3 or 4	Permanently discontinue		
Exfoliative Dermatologic Conditions	Suspected SJS, TEN, or DRESS	Withhold	
 Based on severity of AE administer corticosteroids 	
 Ensure adequate evaluation to confirm etiology or exclude other causes
	Confirmed SJS, TEN, or DRESS	Permanently discontinue		
All other irAEs	Persistent Grade 2	Withhold	
 Based on type and severity of AE administer corticosteroids 	
 Ensure adequate evaluation to confirm etiology and/or exclude other causes
	Grade 3	Withhold or discontinue based on the type of event ^a .		
	Grade 4 or recurrent Grade 3	Permanently discontinue		

AE(s)=adverse event(s); ALT= alanine aminotransferase; AST=aspartate aminotransferase; CTCAE=Common Terminology Criteria for Adverse Events; DRESS=Drug Rash with Eosinophilia and Systemic Symptom; GI=gastrointestinal; IO=immuno-oncology; ir=immune related; IV=intravenous; SJS=Stevens-Johnson Syndrome; T1DM=type 1 diabetes mellitus; TEN=Toxic Epidermal Necrolysis; ULN=upper limit of normal.

Note: Non-irAE will be managed as appropriate, following clinical practice recommendations.

^a AST/ALT: >3.0 to 5.0 x ULN if baseline normal; >3.0 to 5.0 x baseline, if baseline abnormal; bilirubin: >1.5 to 3.0 x ULN if baseline normal; >1.5 to 3.0 x baseline if baseline abnormal

^b AST/ALT: >5.0 to 20.0 x ULN, if baseline normal; >5.0 to 20.0 x baseline, if baseline abnormal; bilirubin: >3.0 to 10.0 x ULN if baseline normal; >3.0 to 10.0 x baseline if baseline abnormal

^c AST/ALT: >20.0 x ULN, if baseline normal; >20.0 x baseline, if baseline abnormal; bilirubin: >10.0 x ULN if baseline normal; >10.0 x baseline if baseline abnormal

^d The decision to withhold or permanently discontinue pembrolizumab is at the discretion of the investigator or treating physician. If control achieved or \leq Grade 2, pembrolizumab may be resumed.

^e Events that require discontinuation include, but are not limited to: encephalitis and other clinically important irAEs (e.g., vasculitis and sclerosing cholangitis).

Dosing interruptions are permitted in the case of medical / surgical events or logistical reasons not related to study therapy (e.g., elective surgery, unrelated medical events, patient vacation, and/or holidays). Subjects should be placed back on study therapy within 3 weeks of the scheduled interruption, unless otherwise discussed with the Sponsor-Investigator or lead sub-investigator. The reason for interruption should be documented in the patient's study record.

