5.4 Rescue Medications & Supportive Care

5.4.1 Supportive Care Guidelines

Subjects should receive appropriate supportive care measures as deemed necessary by the treating investigator. Suggested supportive care measures for the management of adverse events with potential immunologic etiology are outlined below and in greater detail in the ECI guidance document. Where appropriate, these guidelines include the use of oral or intravenous treatment with corticosteroids as well as additional anti-inflammatory agents if symptoms do not improve with administration of corticosteroids. Note that several courses of steroid tapering may be necessary as symptoms may worsen when the steroid dose is decreased. For each disorder, attempts should be made to rule out other causes such as metastatic disease or bacterial or viral infection, which might require additional supportive care. The treatment guidelines are intended to be applied when the investigator determines the events to be related to pembrolizumab.

Note: if after the evaluation the event is determined not to be related, the investigator is instructed to follow the ECI reporting guidance but does not need to follow the treatment guidance (as outlined in the ECI guidance document). Refer to Section 5.2.1 for dose modification.

It may be necessary to perform conditional procedures such as bronchoscopy, endoscopy, or skin photography as part of evaluation of the event. Suggested conditional procedures, as appropriate, can be found in the ECI guidance document.

- **Pneumonitis:**

- For **Grade 2 events**, treat with systemic corticosteroids. When symptoms improve to Grade 1 or less, steroid taper should be started and continued over no less than 4 weeks.
- For **Grade 3-4 events**, immediately treat with intravenous steroids. Administer additional anti-inflammatory measures, as needed.
- Add prophylactic antibiotics for opportunistic infections in the case of prolonged steroid administration.

- **Diarrhea/Colitis:**

Subjects should be carefully monitored for signs and symptoms of enterocolitis (such as diarrhea, abdominal pain, blood or mucus in stool, with or without fever) and of bowel perforation (such as peritoneal signs and ileus).

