- All subjects who experience diarrhea/colitis should be advised to drink liberal quantities of clear fluids. If sufficient oral fluid intake is not feasible, fluid and electrolytes should be substituted via IV infusion. For Grade 2 or higher diarrhea, consider GI consultation and endoscopy to confirm or rule out colitis.
- For **Grade 2 diarrhea/colitis** that persists greater than 3 days, administer oral corticosteroids.
- For **Grade 3 or 4 diarrhea/colitis** that persists > 1 week, treat with intravenous steroids followed by high dose oral steroids.
- When symptoms improve to Grade 1 or less, steroid taper should be started and continued over no less than 4 weeks.

- **Type 1 diabetes mellitus (if new onset, including diabetic ketoacidosis [DKA]) or ≥ Grade 3 Hyperglycemia, if associated with ketosis (ketonuria) or metabolic acidosis (DKA)**

- For **T1DM or Grade 3-4 Hyperglycemia**
 - Insulin replacement therapy is recommended for Type I diabetes mellitus and for Grade 3-4 hyperglycemia associated with metabolic acidosis or ketonuria.
 - Evaluate patients with serum glucose and a metabolic panel, urine ketones, glycosylated hemoglobin, and C-peptide.

- **Hypophysitis:**

- For **Grade 2 events**, treat with corticosteroids. When symptoms improve to Grade 1 or less, steroid taper should be started and continued over no less than 4 weeks. Replacement of appropriate hormones may be required as the steroid dose is tapered.
- For **Grade 3-4 events**, treat with an initial dose of IV corticosteroids followed by oral corticosteroids. When symptoms improve to Grade 1 or less, steroid taper

should be started and continued over no less than 4 weeks. Replacement of appropriate hormones may be required as the steroid dose is tapered.

- **Hyperthyroidism or Hypothyroidism:**

Thyroid disorders can occur at any time during treatment. Monitor patients for changes in thyroid function (at the start of treatment, periodically during treatment, and as indicated based on clinical evaluation) and for clinical signs and symptoms of thyroid disorders.

- **Grade 2** hyperthyroidism events (and **Grade 2-4** hypothyroidism):

- In hyperthyroidism, non-selective beta-blockers (e.g. propranolol) are suggested as initial therapy.
 - In hypothyroidism, thyroid hormone replacement therapy, with levothyroxine or liothyroinine, is indicated per standard of care.

- **Grade 3-4** hyperthyroidism

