Each of the events above is described within this guidance document, along with site requirements for reporting these events to the Sponsor. The information collected should be entered into the narrative field(s) of the Adverse Event module in the database (please note, if narrative entry into the database is not available, please use the narrative text box on the 1727/AER Form). If additional Medical History or Concomitant Medications are reported, the Medical History and Concomitant Medication modules in the database must be updated.

In addition, the guidelines include recommendations on the management of these ECIs. These guidelines are intended to be applied when the physician determines the events to be related to pembrolizumab. Note: if after the evaluation the event is determined not to be related, the physician is instructed to follow the ECI reporting guidance but does not need to follow the treatment guidance (below). Therefore, these recommendations should be seen as guidelines and the treating physician should exercise individual clinical judgment based on the patient. For any question of dose modification or other treatment options, the specific language in the

protocol should be followed. Any questions pertaining to the collection of this information or management of ECIs should be directed to your local Sponsor contact.

Dose Modification/Discontinuation

The treatment guidance provides specific direction when to hold and/or discontinue pembrolizumab for each immune related adverse event. Of note, when the guidance states to “discontinue” pembrolizumab this is the permanent discontinuation of treatment with pembrolizumab. “Hold” means to stop treating with pembrolizumab but resumption of treatment may be considered assuming the patient meets the criteria for resumption of treatment.

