- If IV steroids followed by high dose oral steroids does not reduce initial symptoms within 48 to 72 hours, treat with additional anti-inflammatory measures. Discontinue additional anti-inflammatory measures upon symptom relief and initiate a prolonged steroid taper over 45 to 60 days. If symptoms worsen during steroid reduction, initiate a retapering of steroids starting at a higher dose of 80 or 100 mg followed by a more prolonged taper and administer additional anti-inflammatory measures, as

needed

- Add prophylactic antibiotics for opportunistic infections.

3.2 *Colitis*

The following AE terms, if considered \geq Grade 2 or resulting in dose modification or use of systemic steroids to treat the AE, are considered ECIs and should be reported to the Sponsor within 2 business days of the event:

- Colitis
- Colitis microscopic
- Enterocolitis
- Enterocolitis hemorrhagic
- Gastrointestinal perforation
- Intestinal obstruction
- Necrotizing colitis
- Diarrhea

All attempts should be made to rule out other causes such as metastatic disease, bacterial or parasitic infection, viral gastroenteritis, or the first manifestation of an inflammatory bowel disease by examination for stool leukocytes, stool cultures, a Clostridium difficile titer and endoscopy. However, the AE should be reported regardless of etiology.

Course of Action

Grade 2 Diarrhea/Colitis (4-6 stools/day over baseline, dehydration requiring IV fluids < 2 business days, abdominal pain, mucus or blood in stool):

- Report as ECI
- Hold pembrolizumab.
- Symptomatic Treatment
- For Grade 2 diarrhea that persists for greater than 3 days, and for diarrhea with blood and/or mucus,
- Consider GI consultation and endoscopy to confirm or rule out colitis
- Administer oral corticosteroids (prednisone 1-2 mg/kg QD or equivalent)
- When symptoms improve to Grade 1 or less, steroid taper should be started and continued over no less than 4 weeks.
- Permanently discontinue for inability to reduce corticosteroid dose to 10 mg or less of prednisone or equivalent per day within 12 weeks.
- If symptoms worsen or persist > 3 days treat as Grade 3

Grade 3 Diarrhea/Colitis (or Grade 2 diarrhea that persists for > 1 week):

- Report as ECI

- Hold pembrolizumab.
- Rule out bowel perforation. Imaging with plain films or CT can be useful.
- Recommend consultation with Gastroenterologist and confirmation biopsy with endoscopy.

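### Section 5.4.1 makes steroids for Grade 3 or 4 diarrhea/colitis wait more than a week, longer than for Grade 2 and at odds with Table 3 (Grade 3) and the ECI guidance

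*Combined protocol and SAP*

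**What the plan says.** Three texts in the combined protocol and SAP deal with steroids for diarrhea/colitis.

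- **Section 5.2.1.2, Table 3, Diarrhea/Colitis row, Grade 2 or 3.** Pembrolizumab is withheld and the steroid column reads "Administer corticosteroids (initial dose of 1-2 mg/kg prednisone or equivalent) followed by taper". No duration is attached. (The same words appear in other rows; the Diarrhea/Colitis row is meant here.)
- **Section 5.4.1, Diarrhea/Colitis.** For a Grade 2 event "that persists greater than 3 days, administer oral corticosteroids". For a Grade 3 or 4 event "that persists > 1 week, treat with intravenous steroids followed by high dose oral steroids". The section introduces its content as "Suggested supportive care measures for the management of adverse events with potential immunologic etiology".
- **Appendix 11.5 (ECI guidance), section 3.2 Colitis.** At Grade 2 the steroid trigger is "For Grade 2 diarrhea that persists for greater than 3 days, and for diarrhea with blood and/or mucus". At Grade 3 intravenous steroids are given with no waiting time, and Grade 4 is managed in the same way. The heading of the Grade 3 block also takes in Grade 2 diarrhea lasting more than one week.

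On precedence, the ECI overview says "For any question of dose modification or other treatment options, the specific language in the" protocol is to be followed. The text above Table 3 sends the reader to a section 5.6.1 and to the ECI guidance for supportive care, including corticosteroid use. There is no section 5.6.1; section 5.6 covers withdrawal and discontinuation. Section 5.4.1 refers back to 5.2.1 for dose modification.

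**The concern.** Within 5.4.1 the order of urgency is reversed: the milder event reaches its steroid trigger first. For a Grade 3 event in its first week, or a Grade 2 event in its first three days, a site working from Table 3 would give systemic steroid, while a site working from 5.4.1 would find no suggestion yet to do so. This is an immune toxicity for which both Table 3 and 5.4.1 ask sites to watch for bowel perforation, so unclear timing matters for patient care. Because the ECI overview defers to specific protocol language, a site could also take the one-week wait in 5.4.1 as displacing the immediate treatment that the guidance gives at Grades 3 and 4.

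**Working it through.** No figure in the plan is being reproduced; the check is a comparison of texts. Each cell below says whether the text directs or suggests steroid. A no means that the text does not call for it, not that it forbids it.

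| Grade and duration | Table 3 | Section 5.4.1 | ECI guidance 3.2 |
|---|---|---|---|
| Grade 2, 3 days or less | yes | no | only with blood and/or mucus |
| Grade 2, more than 3 days | yes | yes | yes |
| Grade 3, 1 week or less | yes | no | yes |
| Grade 3, more than 1 week | yes | yes | yes |
| Grade 4, 1 week or less | not assessed | no | yes |
| Grade 4, more than 1 week | not assessed | yes | yes |

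Table 3 is not assessed at Grade 4 because the steroid cell is blank in the text available and may be merged with the cell above it.

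1. **Table 3 against 5.4.1.** Over Grades 2 and 3, split at the durations that 5.4.1 uses, there are 2 × 2 = 4 scenarios. The two texts differ in 2: Grade 2 of 3 days or less, and Grade 3 of 1 week or less.
2. **Order within 5.4.1.** The wait is more than 7 days at Grade 3 or 4 and more than 3 days at Grade 2. The difference is 7 − 3 = 4 days, in the wrong direction for severity.
3. **5.4.1 against the guidance at Grades 3 and 4.** They differ whenever the event has lasted 1 week or less. For Grade 3 the guidance says to consider additional anti-inflammatory treatment if steroids have not reduced symptoms within 48 to 72 hours, that is, 2 to 3 days after starting them. If steroids start at onset, that step falls before 5.4.1 has suggested any steroid at all.
4. **Comparison within 5.4.1.** Its Grade 3 or 4 pneumonitis entry calls for immediate intravenous steroids, and its Grade 3 or 4 hepatic and renal entries set no wait. Diarrhea/colitis is the exception.
5. **Likely source.** The guidance uses a one-week duration once, in the Grade 3 heading, to bring in persistent Grade 2 diarrhea. Attaching that duration to Grade 3 or 4 events would produce the wording in 5.4.1. This is an inference; the documents do not give the origin of the phrase.

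**The case against.** The strongest reply is that the protocol divides the work: 5.2.1.2 governs holding the drug and points elsewhere for steroid use, and 5.4.1 carries the title to which that pointer refers. Part of this stands. Despite the wrong section number, the pointer does direct readers towards supportive care, so it would be too strong to say that nothing connects the two texts. But Table 3 has its own steroid column with a dose, and the pointer does not say that 5.4.1 overrides it. On this reading the one-week wait would govern Grade 3, which is the less desirable result. The general-instructions row of Table 3 is empty in the text available, so the claim is limited to what can be read.

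The second reply is discretion, and it stands as a limit on severity. The 5.4.1 measures are suggestions, section 5.3 leaves the final decision on supportive therapy with the investigator or the subject's primary physician, and the ECI overview asks for individual clinical judgment. Nobody is barred from treating a Grade 3 event on the first day.

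A reader might infer more than the documents support in three ways:

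- **That 5.4.1 cancels the guidance's blood-or-mucus trigger at Grade 2.** The guidance describes Grade 2 as including "dehydration requiring IV fluids < 2 business days, abdominal pain, mucus or blood in stool", and 5.4.1 does not make blood or mucus a steroid trigger. But silence is not the specific protocol language to which the guidance gives way, and 5.4.1 itself refers to the guidance for more detail.
- **That the guidance contradicts itself.** Its Grade 2 block ends with "If symptoms worsen or persist > 3 days treat as Grade 3", while its Grade 3 heading uses one week for Grade 2. The line follows the instruction to start oral steroids after 3 days, so it reads naturally as more than 3 further days despite treatment. That is about 3 + 3 = 6 days from onset, close to the one-week heading.
- **That Table 3 and 5.4.1 disagree in three of six scenarios.** That count splits Grade 2 by blood or mucus, which neither text uses as a steroid condition, and so counts one difference twice.

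**Conclusion.** The point holds, as a minor one. The one-week condition at Grade 3 or 4 in 5.4.1 is out of step with its own Grade 2 rule, with Table 3 at Grade 3, and with the ECI guidance at Grades 3 and 4. The Grade 2 difference between Table 3 and 5.4.1 is real but less clear-cut, since for diarrhea without blood or mucus the guidance agrees with 5.4.1. The conclusion assumes that the unreadable part of Table 3 holds no rule on steroid timing.

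The effect is on consistent patient management. The documents give no incidence of colitis, so the number of patients affected cannot be estimated. The response-rate endpoint, the power and the toxicity suspension rule are not affected; that rule, in section 8.2, counts immune-related or infusional events of Grade 3 or higher and does not refer to steroid timing.

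**What to change.** 1. In 5.4.1, delete the one-week persistence condition from the Grade 3 or 4 diarrhea/colitis sentence and leave the rest of the sentence unchanged. This is the priority edit.
2. Have the clinical team choose one Grade 2 steroid trigger and state it identically in Table 3 and 5.4.1. The guidance's trigger, more than 3 days or the presence of blood and/or mucus, is one ready option.
3. In 5.2.1.2, change the reference to section 5.6.1 to section 5.4.1. This is clerical.

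The cost is a few wording edits in one amendment and one short clinical decision (item 2). No procedures, visits or patients are added.
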